### **2.1.1 PRIMARY OUTCOME – EFFECTS OF PAAP ON PENICILLIN PRESCRIBING**

The primary outcome is the effect of PAAP on penicillin prescribing, and is defined as: the proportion of participants who receive prescriptions for a penicillin when attending for predefined conditions where a penicillin is the first-line recommended antibiotic (see Appendix II) up to 12 months post-randomisation.

The primary outcome will be coded as 1 (“Yes”) if there is evidence of a penicillin prescription during the course of routine care, up to 12 months post randomisation on any of the following data sources: SystmOne report/notes review (Variable *ISPRIMARYEVENT*), patient follow-up calls, or hospital prescribing reports. Participants that have not required penicillin treatment during the trial will have their primary outcome coded as 0 (“No”).

Participants who do not have evidence of a prescription and who withdrew consent for notes review to be conducted, will have their primary outcome missing at 12 months.

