#### **2.1.2.3.1 NUMBER OF ANTIBIOTIC PRESCRIPTIONS**

This outcome will be derived from the notes review question “*Please list all the antibiotics the patient was treated with for the above event or symptoms*” (Variable *ABXNAME*), as well as data from the SystmOne report and hospital prescribing report (if available). This outcome will be derived as the number of antibiotic prescriptions up to 12 months post-randomisation. If there is no evidence of antibiotic usage this outcome will be coded as zero. A “prescription” will be considered to be an uninterrupted period of antibiotic use. Where a period of at least 2 days separates prescriptions for the same antibiotic, these will be considered separate prescriptions.

If the patient had a relevant infection event but there is no prescription data for that patient then this outcome will be missing. Patients who also withdrew before 12 months who do not have an antibiotic prescription, and who withdrew consent for notes reviews to be conducted will also have this outcome missing.

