#### **2.1.2.5 MORTALITY RATES**

Information regarding mortality will be obtained from the 12-month combined notes review question “*Is the participant alive?*” (Variable *ISALIVE*), the SAE report (Variable *SAESER*), the HES database, the ONS database, and the SystmOne report. This outcome will be derived as a binary variable and will be coded as affirmative if there is evidence of death on any of the sources listed above, this outcome will be coded as negative if there is no evidence of death on any of these sources. If there is a contradiction between the sources the participant will be assumed to have died. If a participant had withdrawn consent to note review/follow-up and there is no evidence of a death prior to withdrawal, then this outcome will be missing.

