### 4.1 PRIMARY OUTCOME

The primary outcome is penicillin prescribing, defined as the proportion of participants who receive prescriptions for a penicillin when attending for predefined conditions where a penicillin is the first-line recommended antibiotic up to 12 months post-randomisation. A binomial mixed-effects generalised linear model (MEGLM) with a logit link function will be fitted to the data with penicillin prescribing within 12 months of randomisation, as the dependent variable. The model will include randomised group, age, number of antibiotic prescriptions (as a continuous variable) up to the 24 months prior to randomisation (up to 12 months for those recruited to the nested pilot study), and the number of QOF registered diseases as fixed effects. These variables will come from the clinical database. GP practice will be included as a random effect. The adjusted relative risk between the randomised groups and the corresponding 95% confidence intervals will be obtained from the marginal adjusted relative risk (based on delta-method standard errors (Norton et al. 2013)) between the randomised groups and reported alongside the associated P-value.

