### 4.2 HANDLING MISSING DATA

Missing data will be reported, with reasons where available. The mixed effects regression model assumes data is missing at random (MAR), however the mechanism of missing data will be explored. The baseline characteristics listed in section 3.2 (except those that were patient reported, and the ones from Sortition used in the randomisation) will be summarised for both randomised groups, split depending on if the primary outcome is available or missing. A logistic regression model will explore any association between each baseline characteristic and the availability of the primary outcome. Covariates found to be predictive of missingness ( $P<0.05$ ) will be included in the analysis model in a sensitivity analysis of the primary outcome (see section 6). If the primary outcome is available for all participants this will not be conducted.

Should any covariates (to be included in the model) have missing baseline data, the overall mean of the covariate at baseline will replace the missing values (Sullivan et al. 2018) to enable all randomised participants with outcome data to be included in the analysis.

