## **6.2 FACTORS THAT PREDICT MISSINGNESS**

A logistic regression analysis, described in section 4.2 will be conducted to investigate factors (if any) that are predictive of non-response of the primary outcome. If any factors are associated with non-response, the model used in the primary analysis (section 4.1) will be re-run with these factors included in the model as fixed effects, alongside randomised group, age, number of antibiotic prescriptions in the 24 months prior to randomisation (12 months for those recruited to the nested pilot study), and the number of QOF registered diseases as fixed effects, and GP practice as a random effect. The adjusted relative risk between the randomised groups and the corresponding 95% confidence intervals will be obtained from the model and reported alongside the associated P-value.

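### Participants who withdraw notes-review consent can enter the primary analysis only as a 1, so their missingness depends on the outcome and no baseline adjustment repairs it

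*SAP*

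**What the plan says.** SAP section 2.1.1 has three coding rules for the primary outcome.

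- Code 1 applies "if there is evidence of a penicillin prescription during the course of routine care, up to 12 months post randomisation" in any listed data source. Complete follow-up is not required.
- Code 0: "Participants that have not required penicillin treatment during the trial will have their primary outcome coded as 0".
- Missing: those who "do not have evidence of a prescription and who withdrew consent for notes review to be conducted, will have their primary outcome missing".

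On the analysis, section 4.1 states: "A binomial mixed-effects generalised linear model (MEGLM) with a logit link function will be fitted to the data". Apart from randomised group and the practice random effect, its covariates are all baseline variables. Section 4.2 adds: "The mixed effects regression model assumes data is missing at random (MAR), however the mechanism of missing data will be explored". The exploration relates baseline characteristics to availability of the outcome. Section 6.2 uses a logistic regression "to investigate factors (if any) that are predictive of non-response of the primary outcome" and re-runs the primary model with any such factors added. Section 6.3 re-runs the primary analysis without participants who lack 12 months of follow-up. It is introduced by reference to late recruitment and does not mention withdrawal.

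For the number of prescriptions (2.1.2.3.1), the outcome is also missing for "Patients who also withdrew before 12 months who do not have an antibiotic prescription, and who withdrew consent for notes reviews to be conducted".

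**The concern.** Take two participants in the same arm with the same baseline values, both of whom withdraw notes-review consent at month six. One had a penicillin recorded at month three and stays in the analysis as a 1. The other had none and is removed. Whether each is observed is decided by the outcome itself. This happens even if the reason for withdrawing has nothing to do with prescribing.

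The removed participants are disproportionately zeros, so the penicillin proportion is pushed upwards in each arm. If the two arms withdraw at the same rate, most of the inflation cancels in the relative risk. If they do not, it does not cancel. The trial is open label and only the PAAP arm is asked to attend a clinic for testing, so unequal withdrawal is possible. The adjustment in 6.2 cannot show the problem, because no baseline variable stands in for whether the event had already happened.

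The count outcome follows the same pattern. Withdrawers with at least one prescription keep a count truncated at withdrawal, withdrawers with none are dropped, and the Poisson model in 5.3 has no term for follow-up time.

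**Working it through.** **Inputs from the SAP (2.3 and 2.4).** Planning rates of 4% (usual care) and 14% (PAAP), relative risk 14/4 = 3.50; 50% of participants expected to need a prescription; 10% attrition; 1:1 allocation; 848 participants, 424 per arm, at 90% power.

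**The plan's own figure.** A continuity-corrected two-proportion calculation for 4% v 14% (two-sided 5%) gives 190 per arm at 90% power. Dividing by 0.5 × 0.9 = 0.45 gives 190/0.45 = 422.2, so 423 per arm and 846 in total, against 848 stated. At 80% power it gives 147 per arm and 654 in total, against 656. The planning inputs are therefore read correctly. Since 2.1.1 codes participants who needed no penicillin treatment as 0, the rates among all randomised participants would be about 4% × 0.5 = 2% and 14% × 0.5 = 7%. Both scales are shown below.

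**Assumptions (not in the SAP).** w is the share of an arm withdrawing notes-review consent before 12 months; q is the share of withdrawers' events recorded before they withdraw. Withdrawal is taken as unrelated to outcome, so that only the coding rule is at work. If event and withdrawal times are both spread evenly over the year, q = 0.5.

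**Formulae.**

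- P(missing | outcome 1) = w(1 − q)
- P(missing | outcome 0) = w
- Observed proportion = p(1 − w + wq) / (1 − w + wqp)

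With w = 10% and q = 0.5, missingness is 5% among those with the outcome and 10% among those without. The two are equal only if w = 0 or q = 0.

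**In numbers, PAAP arm, p = 14%.** Of 424 participants, 42.4 withdraw. They have 42.4 × 0.14 = 5.94 events, of which 2.97 are recorded first. Those who stay contribute 381.6 participants and 53.42 events. Observed proportion: (53.42 + 2.97) / (381.6 + 2.97) = 56.39/384.57 = 14.7%. The same calculation for usual care gives 4.2%.

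**Relative risk under the plan's rule (true value 3.50).**

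| Withdrawal, usual care / PAAP | 4% v 14%, q = 0.5 | 4% v 14%, q = 1 | 2% v 7%, q = 0.5 | 2% v 7%, q = 1 |
|---|---|---|---|---|
| 10% / 10% | 3.48 (−0.6%) | 3.46 (−1.1%) | 3.49 (−0.3%) | 3.48 (−0.6%) |
| 2% / 10% | 3.63 (+3.7%) | 3.76 (+7.3%) | 3.64 (+4.1%) | 3.78 (+8.1%) |
| 10% / 2% | 3.35 (−4.2%) | 3.22 (−8.0%) | 3.35 (−4.3%) | 3.22 (−8.1%) |
| 0% / 10% | 3.67 (+4.7%) | 3.83 (+9.4%) | 3.68 (+5.1%) | 3.86 (+10.3%) |
| 10% / 0% | 3.32 (−5.1%) | 3.16 (−9.6%) | 3.32 (−5.2%) | 3.16 (−9.8%) |

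Going beyond planned attrition, 5% v 20% withdrawal with q = 0.5 on the 2% v 7% scale gives 3.81, and the reverse gives 3.20.

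**No true effect, q = 0.5.** At 4% in both arms with 2% v 10% withdrawal, the relative risk is about 1.04. At 7% in both arms with 5% v 20%, it is 1.09.

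**If all of these withdrawers are excluded whatever their outcome,** the observed proportion under the same assumptions is p in each arm and the relative risk returns to 3.50. A simulation with uniform event and withdrawal times agreed: at 4% v 14% with 10% v 2% withdrawal, the plan's rule gave 3.35 and excluding all withdrawers gave 3.50.

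**The case against.** Five points weigh against a stronger reading.

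*Scope.* A reader might infer that every withdrawer is affected. The SAP does not support that. Only withdrawal of notes-review consent triggers the missing code. Other withdrawers are coded from records, and 2.4 keeps PAAP non-attenders in follow-up. This stands, and the point is limited accordingly. The missing rule also says a prescription, not a penicillin prescription. The preceding sentences make penicillin the natural reading, and on the wider one missingness still depends on the outcome.

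*Section 6.3.* Read literally, this re-run already drops withdrawers coded 1 and so removes the asymmetry. But its stated reason is late recruitment, and it does not say whether someone who withdrew after an event is excluded. It is a remedy only once that is written down.

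*Missing at random.* One might say the assumption is false in every sense. That goes too far. If withdrawal is unrelated to later prescribing, missingness depends only on history observed up to withdrawal, which is missing at random given that history. The failure is that a 12-month binary model with baseline covariates does not use the history.

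*Mortality.* The rule in 2.1.2.5 looks parallel, since for those who withdrew, if "there is no evidence of a death prior to withdrawal, then this outcome will be missing". But nobody withdraws consent after dying, so this wording cannot keep a withdrawer as a death. The asymmetry is absent.

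*Size.* A reader might fear a false positive trial. In the extreme no-effect case above (7%, 5% v 20%, 424 per arm), the bias in the log relative risk is 0.085 against a standard error of about 0.26, which raises a two-sided 5% error rate to about 6%. With a true relative risk of 3.50, none of the scenarios changes the conclusion.

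**Conclusion.** The point holds for participants who withdraw notes-review consent. Section 2.1.1 lets them in as 1 and never as 0, the missing-at-random statement in 4.2 is wrong for them under the model chosen, and 6.2 cannot repair it. The direction is certain for each arm's proportion, which is biased upwards. The effect on the relative risk is about 1% or less when withdrawal is balanced at up to 10%. It reaches roughly 10% in either direction when withdrawal lies between 0 and 10% and differs strongly by arm. These sizes rest on assumed w and q; the SAP gives only the 10% attrition figure and no count of notes-review withdrawals. The prescription count shares the defect; mortality does not. The bias is modest, but it affects the primary outcome, and no planned analysis is worded so that it would clearly reveal it.

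**What to change.** 1. In 6.3, state that everyone who withdrew notes-review consent before 12 months is excluded from that re-run whatever their outcome, so that availability is defined by follow-up.
2. Add a sensitivity analysis of the 12-month penicillin proportion, or of time to first penicillin for a listed condition. Include all randomised participants in the analysis population in their allocated arm, censor at withdrawal of notes-review consent or data cut, and state how death is handled. This uses the history up to withdrawal. It still assumes that withdrawal is unrelated to later prescribing, and the SAP should say so.
3. Correct 4.2 to say that under the 2.1.1 coding the outcome is not missing at random given baseline covariates for this group, and point to items 1 and 2.
4. For the prescription count, keep all participants up to withdrawal and add the log of follow-up time as an offset.

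A bound that sets every missing outcome to 1 is not worth adding. With 10% missing it would add about 42 events per arm of 424, against about 8 expected at 2% and 30 at 7%.

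Cost: small extra analysis work and a few events lost from the 6.3 re-run. The primary model is unchanged. The sponsor should confirm that dates of consent withdrawal are held, because the SAP names prescription dates but not these.

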### **2.1.2 SECONDARY OUTCOMES**

#### **2.1.2.1 TREATMENT “RESPONSE FAILURE”**

Treatment “response failure” defined as: re-presentation with worsening or non-resolving or new symptoms (related to the index infection) following treatment with an antibiotic up to 28 days after initial antibiotic prescription (including re-prescription of antibiotic within 28 days of an index prescription) for predefined infections (collected from the SystmOne report, patient symptom diaries, and post antibiotic telephone call). Treatment “response failure” will be coded as 1 (“Yes”) if the patient went back to the GP because symptoms worsened, or if the symptoms did not resolve, or if new symptoms developed, this information is collected from the symptom diary. This outcome will also be coded as 1 (“Yes”) if the participant had a new antibiotic prescribed on the day 28-30 post antibiotic telephone call (Variable *REPRESYN*) for the same index condition, or if there is evidence of a re-prescription on the SystemOne report and this was confirmed as a treatment response failure on notes review. Participants who have no evidence of a treatment “response failure” on any of these data sources, will have this outcome coded as 0 (“No”). Participants who withdrew before 12 months with no prescription event and who withdrew consent for notes review to be conducted will have this outcome missing.

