### **2.1.2.2 DURATION OF SYMPTOMS RATED ‘MODERATELY BAD’ OR WORSE**

The predominant symptoms are scored daily on a scale from 0 to 6 (0 = no problem, 1 = very little problem, 2 = slightly problem, 3 = moderately bad, 4 = bad, 5 = very bad, and 6 = as bad as it could be). The scale is taken from a validated measure (Watson et al. 2001). The duration of symptoms rated ‘moderately bad’ or worse by patients after antibiotic treatment will be derived from the day 1-28 symptom diary question “*Tell us how bad these symptoms are today by ticking the box for your chosen number that fits best with how you are feeling*” which is completed after each antibiotic prescription. The number of days the patient answered, “moderately bad” (score = 3), “bad” (score = 4), “very bad” (score = 5), or “as bad as it could be” (score = 6) for the first antibiotic prescription event from the diaries will be calculated.

If the patient did not complete all their symptom diaries the day 28-30 post antibiotic telephone call will be used. At the day 28-30 call, participants are asked if their symptoms have resolved, and if they did resolve, how many days did it take for the symptom to become a minor problem or less (Variables *SYMP1RESLV SYMP2RESLV SY1RESLNUM SY2RESLNUM*). If the patient indicated on the call that the symptom did not resolve this outcome will be coded as 28 days.

If a patient had a prescription event that required diary completion, but they did not fill out any diaries or complete the 28-30 call this outcome will be missing.

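### Response failure is coded 0 rather than missing when a participant had an index prescription but no diary, day 28-30 call or notes review

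*SAP*

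**What the plan says.** SAP 2.1.2.1 gives three routes to a score of 1:

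- The participant went back to the GP because symptoms had worsened, persisted or newly appeared. For this route, "this information is collected from the symptom diary".
- A new antibiotic for the same condition was reported on the day 28-30 call.
- The records show it, that is, "if there is evidence of a re-prescription on the SystemOne report and this was confirmed as a treatment response failure on notes review".

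Participants with no evidence of failure "on any of these data sources, will have this outcome coded as 0". The section has one missing rule, for those who "withdrew before 12 months with no prescription event and who withdrew consent for notes review to be conducted will have this outcome missing".

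Other outcomes in section 2.1 treat lack of observation differently. For symptom duration (2.1.2.2), if a diary was due "but they did not fill out any diaries or complete the 28-30 call this outcome will be missing". For the prescription count (2.1.2.3.1), "If the patient had a relevant infection event but there is no prescription data for that patient then this outcome will be missing". The primary outcome (2.1.1), mortality (2.1.2.5) and 3-month de-labelling (2.1.2.8) are missing when the event was not seen and the relevant consent had been withdrawn.

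**The concern.** A prescription plays a different part in this outcome than in its neighbours. For the primary outcome and the prescription count, a prescription is itself evidence on the outcome, so making missingness conditional on there being none is sensible. For response failure, a prescription only opens the 28-day window in which failure can occur. The parallel condition would be that no failure was seen. As written, some withdrawers never seen to be at risk become missing, while participants known to be at risk but not observed become successes.

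Response failure was the trial's initial primary outcome (2.3) and is now the first-listed secondary. The trial is open label, and PAAP participants receive extra calls after testing (section 9), so equal engagement with diaries and calls cannot be taken for granted. The direction of any difference is unknown. Coding 0 also keeps these participants out of the missing-data counts. The missingness work in 4.2 and the sensitivity analyses specified in section 6 concern the primary outcome, so nothing planned would show the effect.

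**Working it through.** **Running one case through the rule.** Take a participant with an index prescription, no diary, no day 28-30 call and no notes review.

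| Step in 2.1.2.1 | Result |
|---|---|
| Re-presentation, from the diary | No diary, so cannot score 1 |
| New antibiotic, from the call | No call, so cannot score 1 |
| Re-prescription on SystmOne | Counts only after notes-review confirmation, so cannot score 1 |
| Missing rule | Requires no prescription event; there was one, so not met |
| Residual rule | Coded 0 |

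Reading 'prescription event' as re-prescription would not be natural. Section 2.1.2.2 uses the same term for the antibiotic prescription that triggers the diary.

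**The plan's own figures.** The coding rule carries no figure. Section 2.3 gives 19.8% v 11.9% for the initial primary outcome, with totals of 1592 and 2090. A continuity-corrected two-proportion calculation gives 360 and 473 per arm at 80% and 90% power. Then 2 × 360 / 0.5 / 0.9 = 1600 and 2 × 473 / 0.5 / 0.9 = 2102, within 0.6% of the stated totals. Section 2.3 defines these rates on re-prescription only, so they are not failure rates for the wider outcome in 2.1.2.1 and are not used as such below.

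**Effect on the relative risk.** Let q be the share with an index prescription, r the true failure risk among them, and m the share of them with no source at all. Assume lack of observation is unrelated to failure within arm. Under the current rule the expected observed proportion is q × r × (1 − m), so

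observed RR = true RR × (1 − m_PAAP) / (1 − m_usual care).

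This needs no value for r. The SAP does not give m; every value below is an assumption.

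- Equal m in both arms: factor 1. Each arm's rate, and so the risk difference, shrinks by (1 − m).
- m of 5% (PAAP) v 2% (usual care): 0.95 / 0.98 = 0.97. Reversed: 0.98 / 0.95 = 1.03.
- m of 30% v 10%: 0.70 / 0.90 = 0.78. Reversed: 0.90 / 0.70 = 1.29.

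**What coding them missing achieves.** Among participants with an index prescription, the expected rate returns to r under the same assumption. In an analysis of all randomised participants, those never prescribed stay at 0, so the expected proportion is q × r × (1 − m) / (1 − q × m). With q = 0.5, the planning share in 2.3:

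- 5% v 2%: (0.95 / 0.975) / (0.98 / 0.99) = 0.98, against 0.97 under the current rule.
- 30% v 10%: (0.70 / 0.85) / (0.90 / 0.95) = 0.87, against 0.78.

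The recode removes roughly half of the distortion in that analysis, which is one reason to report the counts by arm as well.

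**The case against.** The strongest reply is that the wholly unobserved case needs four things together: an index prescription, no diary, no call and no notes review. SAP section 2 says that health records were reviewed at the end of follow-up and that all participants had case-note review. Coding 0 when reviewed records show no event is ordinary practice. Symptom duration is also a weaker comparator than it looks, because it has no record-based source. And the planned effect measure is a relative risk, which is unaffected when the unobserved share is equal by arm. All of this stands. It limits the size of the problem but does not make the rule right for the participants it does reach.

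A reader might go further and infer that anyone who returns no diary and misses the call is counted as a treatment success. The SAP does not support that, because re-prescription can still be found through SystmOne with notes review. Nor is it settled that a non-returner can fail only by re-prescription. The operational sentence in 2.1.2.1 names the diary for re-presentation, but the definition in the same section also lists the SystmOne report, and Appendix I lists notes review. That is an ambiguity to reconcile.

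A reader might also put a size on the stronger reading. With 19.8% in both arms, half of failures visible only by diary or call, and 10% v 30% without either, the rates are 0.198 × (1 − 0.5 × 0.1) = 18.8% and 0.198 × (1 − 0.5 × 0.3) = 16.8%, a gap of 2.0 points. That calculation should not be used here. It describes participants whose records are available, whom the recode would leave at 0. It applies a re-prescription-only rate to a wider outcome, and its shares have no basis in the SAP.

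**Conclusion.** The missing rule in 2.1.2.1 is wrong as written, in a narrow form. It scores as non-failures those participants who had an index prescription and for whom no source was observed, and it is out of line with 2.1.1, 2.1.2.2, 2.1.2.3.1, 2.1.2.5 and 2.1.2.8. The number affected is not given and is probably small. If the unobserved share is the same in both arms, the relative risk is unaffected and only the absolute rates fall. If it differs, the factor on the relative risk is about 0.97 to 1.03 for shares of 2% and 5%, and 0.78 to 1.29 for shares of 10% and 30%. The wider range looks unlikely for this group given default record review. These figures rest on assumed shares and on lack of observation being unrelated to failure. The SAP gives no evidence that the shares do differ by arm.

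**What to change.** - In 2.1.2.1, code the outcome missing when there was an index prescription, no evidence of failure, and no diary, no day 28-30 call and no notes review covering the 28 days. Keep 0 where at least one source covers the window.
- Report the number of such participants by arm.
- Reconcile the sentence that takes re-presentation from the diary with Appendix I, which also lists notes review, and state which sources count.
- Add one sensitivity analysis for this outcome that uses only record-based re-prescription confirmed on notes review. It does not depend on diary or call completion.

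The cost is a changed derivation line, slightly more missing data and one extra analysis. No new data collection is needed.
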